#### **9.4.1.1. Analysis of the Primary Endpoint**

The primary endpoint is the change between baseline and on-treatment liver biopsy (Week 40) in terms of the proportion of HBsAg positive hepatocytes. The primary endpoint will be summarized descriptively and modelled with an appropriate statistical model accounting for the number of hepatocytes sampled in each liver biopsy. The change from baseline will be summarized for the overall study population and within each panel, together with the between-panel difference in the change..

No imputation rule will be applied for the analysis on the ITT population since only complete cases will be considered. In addition, the treatment policy strategy will be followed to account for the occurrence of intercurrent events, such as treatment discontinuation prior to Week 40, ie, all biopsies collected at Week 40 will be used, regardless of occurrence of treatment discontinuation prior to Week 40. This strategy is supported by the small sample size, the exploratory nature of the study and ethical considerations.

In addition, a sensitivity analysis on the ITT population will be combining a treatment policy strategy with the Baseline Observation Carried Forward (BOCF) approach.

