5.1.7. Level of Significance

Due to the exploratory nature of this study, no formal statistical test will be performed. Two-sided 80% CI will be provided with the summary statistics. No adjustment for multiple CIs will be made.

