5.3.1.1. Definition of Endpoint

The primary endpoint for Panels 1 and 2 is defined as the change in the proportion of HBsAg+ hepatocytes between baseline and on-treatment Week 40.

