5.3.1.2.2. Primary Analysis of the Primary Endpoint

5.3.1.2.2.1. Overall Analysis

The change from baseline in proportion of HBsAg+ hepatocytes at Week 40 will be estimated overall – pooling Panels 1 and 2 – by modelling the proportion of HBsAg+ hepatocytes using a binomial mixed model with normal random effects to account for potential overdispersion (Kassahun et al 2012). The potential for overdispersion is supported by preliminary off-treatment results on chronic hepatitis B donors (Sources: Commercial biospecimen sources from Avaden Biospecimen and BioIVT as well as from a pilot phase of phase 0 study NOPRODHPB0012; hereafter referred to as the “donors data”).

The binomial mixed model will model the number of HBsAg+ hepatocytes for each participant at each time point as follows:

$$\begin{aligned}
 Y_{ij} &\sim \text{Binomial}(N_{ij}, p_{ij}) \\
 \text{logit}(p_{ij}) &= \underbrace{(\alpha + \xi_i)}_{\text{intercept}} + \underbrace{(\beta + \gamma_i)j}_{\text{slope}} \\
 &\text{for subject } i = 1, \dots, n \text{ and} \\
 &\text{visit } j = 0 \text{ (for baseline) or } 1 \text{ (for Week 40)} \\
 \xi_1, \dots, \xi_n &\stackrel{\text{iid}}{\sim} N(0, \text{SD}_{\text{intercept}}) \\
 \gamma_1, \dots, \gamma_n &\stackrel{\text{iid}}{\sim} N(0, \text{SD}_{\text{slope}})
 \end{aligned}$$

with:

- Y_{ij} : number of HBsAg+ hepatocytes of subject i at visit j
- N_{ij} : total number of hepatocytes sampled from subject i at visit j
- p_{ij} : probability of a hepatocyte being HBsAg+ for subject i at visit j
- α : Fixed intercept (baseline log-odds of a hepatocyte being HBsAg+) for a “typical” subject, i.e., a subject whose random intercept and slope both equal 0
- ξ_i : Subject-specific random effect for overdispersion of the intercept
- β : Fixed slope (change in the log-odds from baseline to Week 40) for a “typical” subject

- γ_i : Subject-specific random effect for overdispersion of the slope
- n : total number of patients

The input data for this model are Y_{ij} , N_{ij} , and n . There are four parameters to estimate: α , β , $SD_{\text{intercept}}$, and SD_{slope} .

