ATTACHMENT 1. SIMULATIONS FOR SAMPLE SIZE JUSTIFICATION

We conducted a simulation study to assess the expected precision in our estimates of the primary efficacy endpoint if we achieve the target sample size of 24 participants across Panels 1 and 2, and further how the precision would decrease with only 20 or 16 participants.

Assumptions of the Data-Generating Model

We simulated data according to the binomial mixed model as specified in Sections 5.3.1.2.2.1 and 5.3.1.2.2.2. We used the logit model specified in Section 5.3.1.2.2.2 to allow for between-panel differences in the intercept (baseline estimate) and slope (change from baseline):

$$\text{logit}(p_{ij}) = \underbrace{[\alpha + \delta_\alpha I(\text{panel}_i = 1) + \xi_i]}_{\text{intercept}} + \underbrace{[\beta + \delta_\beta I(\text{panel}_i = 1) + \gamma_i] j}_{\text{slope}}$$

where p_{ij} is the probability of a hepatocyte being HBsAg+ for subject i at visit j .

Datasets were simulated with either 16, 20, or 24 subjects (split between two equal-sized panels), and where we varied two aspects of the data:

- The true proportions of HBsAg+ hepatocytes for each panel at each time point. These are specified indirectly by setting the values of α , δ_α , β , and δ_β . See Table 10 for the list of scenarios. Generally, the true proportions at baseline were assumed to be higher in Panel 1 than in Panel 2 because Panel 1 subjects are untreated at baseline.
- The true inter-subject variability of the slope, SD_{slope} , where $\gamma_i \sim N(0, SD_{\text{slope}})$. For each scenario listed in 10, we examined the effect of setting SD_{slope} to 0.5, 1.0, or 2.0.

Table 10: List of scenarios for assumptions on the true proportion of HBsAg+ hepatocytes for each panel at each time point

Scenario ID	Group	% HBsAg+ hepatocytes		Reduction from baseline		Between-panel (1-2) difference in reduction from baseline	
		Baseline	Week 40	Absolute	Relative	Absolute	Relative
A	Panel 1	75%	5%	70%	93.3%	41%	-3.3%
	Panel 2	30%	1%	29%	96.7%		
	Overall	52.5%	3%	49.5%	94.3%		
B	Panel 1	75%	5%	70%	93.3%	50%	26.7%
	Panel 2	30%	10%	20%	66.7%		
	Overall	52.5%	7.5%	45%	85.7%		
C	Panel 1	60%	20%	40%	66.7%	20%	0%
	Panel 2	30%	10%	20%	66.7%		
	Overall	45%	15%	30%	66.7%		

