The 80% CI widths are presented in Figure 3 and again, together with point estimates and 80% CI limits, in Table 11. Generally, we see little bias in the point estimates – the average estimated reductions and differences in reductions in Table 11 match well with the scenario assumptions in 10. This is as expected, as binomial mixed models were used to both simulate the data and carry out the estimation.

The precision of the estimates are of course greater – meaning narrower CIs – with 12 patients per panel than with either 8 or 10 patients. However, the loss in precision with fewer patients is not large in the simulated scenarios, as shown in Figure 3. E.g., in Scenario A with $SD_{slope} = 1.0$, as the sample size per panel increases from 8 to 12 the width of the 80% CI decreases from 20.3% to 16.7% for the overall absolute reduction from baseline; and from 21.8% to 18.1% for the between-panel difference in the absolute reduction.

For the overall absolute reduction (OAR) from baseline, varying the value of SD_{slope} has minimal impact on the CI widths. Across Scenarios A, B, and C, the CI widths vary from roughly 8% to 17% with 12 patients per panel and from 10% to 21% with 8 patients per panel. Generally, the CI widths appear to be larger when the true OAR is larger.

For the overall relative reduction (ORR) from baseline, both the value of SD_{slope} and the scenario assumptions (A, B, or C) have large impacts on the CI widths. In Scenario A the precision was

[figure not shown]
excellent regardless of the value of SD_{slope} , but in Scenario C the precision is both worse and highly dependent on the value of SD_{slope} . In contrast with the OAR, the CI widths for the estimated ORR appear to be larger when the true ORR is smaller.

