Scenario ID	SDslope	Sample size per panel	Overall reduction from baseline (80% CI) [width of 80% CI]		Between-panel (1-2) difference in reduction from baseline (80% CI) [width of 80% CI]	
			Absolute (%)	Relative (%)	Absolute (%)	Relative (%)
A	0.5	8	50.6 (40.5,60.8) [20.3]	95.7 (94.5,97.0) [2.4]	39.4 (28.8,50.0) [21.2]	-3.5 (-6.2,-0.8) [5.4]
		10	50.7 (41.8,59.7) [17.9]	95.7 (94.6,96.8) [2.2]	39.2 (29.6,48.9) [19.3]	-3.4 (-5.8,-1.0) [4.8]
		12	50.8 (42.5,59.1) [16.7]	95.7 (94.7,96.7) [2.0]	40.4 (31.5,49.2) [17.6]	-3.5 (-5.8,-1.3) [4.5]
	1.0	8	50.7 (40.6,60.8) [20.3]	95.6 (93.8,97.3) [3.5]	39.1 (28.2,50.0) [21.8]	-3.6 (-7.7,0.5) [8.3]
		10	50.4 (41.3,59.5) [18.2]	95.6 (94.1,97.2) [3.1]	39.3 (29.4,49.2) [19.8]	-3.5 (-7.1,0.2) [7.4]
		12	50.9 (42.5,59.3) [16.7]	95.7 (94.3,97.1) [2.8]	40.2 (31.1,49.2) [18.1]	-3.6 (-6.9,-0.3) [6.7]
	2.0	8	50.4 (40.2,60.6) [20.5]	95.1 (91.9,98.4) [6.5]	38.4 (26.1,50.7) [24.6]	-4.2 (-12.9,4.4) [17.3]
		10	50.3 (41.2,59.5) [18.4]	95.4 (92.6,98.1) [5.5]	39.6 (28.8,50.4) [21.6]	-3.7 (-10.8,3.5) [14.3]
		12	50.8 (42.5,59.2) [16.7]	95.5 (93.0,98.0) [4.9]	39.7 (29.9,49.6) [19.6]	-3.8 (-10.1,2.6) [12.7]
B	0.5	8	45.7 (36.9,54.5) [17.6]	86.4 (79.8,93.1) [13.3]	49.1 (40.7,57.4) [16.7]	27.0 (19.2,34.8) [15.5]
		10	45.7 (37.8,53.6) [15.8]	86.5 (80.5,92.4) [11.9]	49.8 (42.5,57.2) [14.8]	26.9 (19.9,34.0) [14.1]
		12	45.8 (38.6,52.9) [14.3]	86.5 (81.2,91.9) [10.7]	49.4 (42.5,56.3) [13.8]	27.0 (20.6,33.4) [12.8]
	1.0	8	45.6 (36.5,54.7) [18.1]	86.0 (78.3,93.7) [15.5]	49.4 (39.9,58.9) [19.0]	28.0 (13.3,42.7) [29.3]
		10	45.6 (37.5,53.7) [16.2]	86.3 (79.6,93.1) [13.5]	49.3 (40.8,57.9) [17.1]	27.6 (14.6,40.6) [26.0]
		12	45.7 (38.3,53.1) [14.8]	86.4 (80.3,92.5) [12.2]	49.6 (41.9,57.4) [15.5]	27.3 (15.6,39.1) [23.6]
	2.0	8	44.7 (34.5,55.0) [20.5]	85.1 (74.1,96.1) [22.0]	50.0 (36.1,63.9) [27.8]	31.7 (1.0,62.5) [61.5]
		10	45.2 (36.2,54.2) [18.0]	85.5 (76.0,95.0) [19.0]	49.5 (37.4,61.6) [24.2]	29.6 (3.1,56.1) [52.9]
		12	45.8 (37.6,53.9) [16.2]	85.9 (77.4,94.4) [17.0]	49.4 (38.4,60.4) [21.9]	28.9 (5.3,52.5) [47.2]
C	0.5	8	29.9 (24.8,35.1) [10.3]	67.6 (61.5,73.8) [12.3]	19.0 (11.4,26.7) [15.3]	0.1 (-11.0,11.1) [22.1]
		10	29.9 (25.3,34.6) [9.3]	67.6 (62.1,73.1) [11.1]	19.7 (12.9,26.5) [13.6]	-0.2 (-10.2,9.9) [20.1]
		12	30.0 (25.8,34.2) [8.4]	67.7 (62.7,72.8) [10.0]	19.5 (13.3,25.8) [12.5]	0.1 (-9.0,9.3) [18.3]
	1.0	8	29.7 (23.3,36.0) [12.7]	66.8 (56.8,76.8) [20.0]	19.0 (8.2,29.7) [21.5]	0.4 (-19.1,19.9) [39.0]

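### The primary model reports the change for a typical participant; on the plan's own assumptions its 80% intervals mostly miss the study-population relative change and the Panel 1 absolute change

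*SAP*

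**What the plan says.** The endpoint in SAP 5.3.1.1 is "defined as the change in the proportion of HBsAg+ hepatocytes between baseline and on-treatment Week 40", without saying whether that means a population average or one participant's change. SAP 5.3.1.2.2 fits a binomial mixed model with normal random intercepts and slopes. It then takes p0 = expit(α) and p1 = expit(α + β), and reports their difference and relative change. The fixed intercept and slope are explained as those of a typical participant: "a subject whose random intercept and slope both equal 0". The between-panel model uses the same rule, and the NLMIXED code in Attachment 3 has no step that averages over the random effects.

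Protocol 9.4.1.1 describes the output differently: "The change from baseline will be summarized for the overall study population and within each panel".

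Two other provisions bear on the point. SAP 5.3.1.2.3 plans a secondary, descriptive summary of each participant's observed change, overall and by panel. On intervals, SAP 5.1.7 states: "Two-sided 80% CI will be provided with the summary statistics".

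**The concern.** The expit function is not linear. The proportion for a participant at the centre of the logit distribution is therefore not the mean proportion across participants. Averaging over participants pulls a high baseline such as 75% down and a low Week 40 value such as 5% or 1% up. The plan assumes an intercept SD of 1.0 and slope SDs from 0.5 to 2.0, which is enough spread for the two quantities to separate visibly.

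If the typical-participant figure is read as the study population's change, the relative reduction will look larger, and its interval much tighter, than the population data support. The Attachment 1 simulation cannot reveal this, because its reference values are themselves typical-participant values.

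**Working it through.** **Inputs (SAP Section 3 and Attachment 1).** Intercept SD is 1.0 and slope SD is 0.5, 1.0 or 2.0. There are about 22,000 hepatocytes per biopsy. On sample size: "Datasets were simulated with either 16, 20, or 24 subjects", in two equal panels. Typical proportions from baseline to Week 40 are:

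- Scenario A: 75% to 5% in Panel 1, 30% to 1% in Panel 2
- Scenario B: 75% to 5%, 30% to 10%
- Scenario C: 60% to 20%, 30% to 10%

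Three scenarios, three slope SDs and three sample sizes give 27 settings.

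**Reproducing the plan's figures.** With this many cells binomial noise is negligible, so the fit reduces to the mean baseline logit and the mean logit change. Delta-method intervals used t on n − 2 degrees of freedom, assumed to be the NLMIXED default. For Scenario A, slope SD 0.5, 12 per panel, 20,000 simulated trials gave:

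- overall absolute 50.8%, width 16.5 (SAP: 50.8%, 16.7)
- between-panel absolute 40.1%, width 17.6 (SAP: 40.4%, 17.6)
- overall relative 95.7%, width 2.0 (Table 11: "95.7 (94.7,96.7) [2.0")

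**Population values.** The population mean at a visit is E[expit(μ + σZ)], with Z standard normal and μ the logit of the typical proportion. At baseline σ = 1.0; at Week 40 σ = √(1.0² + SD_slope²). For Scenario A at slope SD 0.5, the Week 40 σ is √1.25 = 1.118, and numerical integration gives:

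- Panel 1: 71.4% to 7.85%, a reduction of 63.6% (typical value 70%)
- Panel 2: 33.1% to 1.78%, a reduction of 31.3% (typical value 29%)
- Overall means: (71.4 + 33.1)/2 = 52.25% and (7.85 + 1.78)/2 = 4.815%
- Overall absolute reduction: 52.25 − 4.815 = 47.4%
- Overall relative reduction: 1 − 4.815/52.25 = 90.8%

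**Scenario A by slope SD.**

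| SD_slope | Overall relative, Table 11 (12 per panel) | Population | Panel 1 absolute, typical | Population | Panel 1 coverage (10 per panel) |
|---|---|---|---|---|---|
| 0.5 | 95.7% | 90.8% | 70% | 63.6% | 44% |
| 1.0 | 95.7% | 88.6% | 70% | 61.9% | 37% |
| 2.0 | 95.5% | 80.4% | 70% | 56.4% | 23% |

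Coverage of the population overall relative change in Scenario A is 0 to 2%. For Panel 1 in Scenario C, the typical 40% compares with 33.7%, 31.8% and 27.1%.

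**Share of nominal 80% CIs that contain the population value, all 27 settings.**

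| Quantity | Coverage | Settings below 50% |
|---|---|---|
| Overall relative | 0–39% | 27 |
| Panel 1 absolute | 17–56% | 23 |
| Panel 2 relative | 3–45% | 27 |
| Panel 1 relative | 14–54% | 24 |
| Overall absolute | 24–85% | 8 |
| Panel 2 absolute | 48–77% | 2 |
| Between-panel absolute | 44–78% | 3 |

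In the stated sample-size case (Scenario A, slope SD 0.5), overall absolute coverage is 83 to 85%. One reason is that the pooled model omits panel. The gap between the panels' baseline logits then enters the intercept spread: half of (1.099 + 0.847) is 0.973, and √(1 + 0.973²) = 1.395 in place of 1.0, which widens the interval.

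**A separate pooling effect.** Attachment 1 includes a table headed "Table 10: List of scenarios for assumptions on the true proportion of HBsAg+ hepatocytes for each panel at each time point". Its Scenario A overall relative reduction is 94.3%. Table 11's three average CIs at slope SD 0.5 (94.5–97.0, 94.6–96.8, 94.7–96.7) all lie above it. Averaging the panels' logits without any random effects already explains this: expit(0.126) = 53.1% and expit(−3.770) = 2.25%, so the relative reduction is 1 − 2.25/53.1 = 95.8%.

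**The case against.** The SAP labels its target as typical throughout 5.3.1.2.2, and a participant-specific effect is a recognised output of a logistic mixed model. For that target the within-panel intervals are sound: they cover the typical change in 76 to 81% of trials in all 27 settings. Low coverage of a different quantity is not a fault in the interval. The descriptive analysis in 5.3.1.2.3, with the 80% CI that 5.1.6 attaches to continuous summaries, will show the mean absolute change anyway. The study is exploratory, with no hypothesis or threshold. The SAP also calls slope variability unknown, and the largest gaps need an SD of 2.0.

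Most of this stands and lowers the severity. What remains is that the protocol promises the study-population change. The planned descriptive mean also gives no population relative change, which is where coverage is worst, even at slope SD 0.5.

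Four stronger readings are not supported:

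- That the primary CIs usually miss the population change in general. This fails for the overall absolute change, the Panel 2 absolute change and nearly all between-panel absolute settings.
- That the model always overstates the reduction. In Scenario A, Panel 2, it understates: 29% against 31.3% and 30.7% at slope SDs of 0.5 and 1.0.
- That Table 11 lying above 94.3% proves the random-effects point. That gap comes from pooling on the logit scale, and 94.3% is itself not a population mean.
- That the plan leaves open which estimate ranks first. Sections 5.3.1.2.2 and 5.3.1.2.3 name one primary and the other secondary.

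**Conclusion.** The point holds for the relative changes and for Panel 1's absolute change. The primary estimates answer a typical-participant question, while protocol 9.4.1.1 poses a population one. In the stated sample-size case the differences are 95.7% against 90.8% for the overall relative reduction, 70% against 63.6% for Panel 1, and 41% against 32.2% for the between-panel absolute difference (coverage 52 to 59%). The overall absolute change is adequately covered there.

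This rests on the SAP's own variance assumptions, equal panels, independent random effects, and the population relative change taken as a ratio of means. Using the mean of individual relative changes instead, overall coverage is 1 to 50%, so the conclusion is unchanged.

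Separately, the Attachment 1 statement "Generally, we see little bias in the point estimates" needs a qualification for the Scenario A overall relative reduction at slope SD 0.5.

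This is a worthwhile improvement rather than an essential correction, since nothing is tested or decided on the estimate.

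**What to change.** In SAP 5.3.1.2.2 and Attachment 3, add population-averaged absolute and relative changes with 80% CIs. Integrate the panel model over its random effects within each panel, and average the two panels for the overall figure. The integrals should be written in terms of the estimated SDs, so that their uncertainty enters the interval. For the absolute change, the mean participant change from 5.3.1.2.3 with a t-based 80% CI is a simple alternative; it covered in about 78 to 81% of simulated trials. Interpret the study-population change from these estimates, and label the random-effects-zero results as typical-participant values.

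In Attachment 1, qualify the bias sentence as described and say that the gap arises from pooling on the logit scale. Coverage of the integrated estimate was not simulated here; the Attachment 1 program can be extended to check it.

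The cost is SAP wording and a few lines of code, with no new data. The downside is that most reported reductions will be smaller.

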5.3.1.2.3. Secondary Analysis of the Primary Endpoint

A secondary, descriptive analysis of the primary endpoint will be conducted. For each participant *i* at visit *j* (0 for baseline; 1 for Week 40), the observed proportion of HBsAg⁺ hepatocytes will be calculated as $P_{ij}^{\text{Obs}} = Y_{ij}/N_{ij}$, where Y_{ij} and N_{ij} are the number of HBsAg⁺ hepatocytes and the total number of evaluated hepatocytes from the biopsy sample, respectively.

The change from baseline to Week 40 will then be calculated for each participant as $\Delta_i^{\text{Obs}} = P_{i1}^{\text{Obs}} - P_{i0}^{\text{Obs}}$. The distributions of the P_{i0}^{Obs} , P_{i1}^{Obs} , and Δ_i^{Obs} across the participants will be described, both overall and by panel. Graphical displays may be used, including spaghetti plots (connecting P_{i0}^{Obs} to P_{i1}^{Obs}) and boxplots.

In addition, scatterplots displaying Y_{ij} versus N_{ij} will be provided.

5.3.1.2.4. Sensitivity Analyses

5.3.1.2.4.1. Baseline Observation Carried Forward (BOCF)

The primary and secondary analyses of the primary endpoint will be repeated by imputing any missing count of HBsAg+ hepatocytes at Week 40 (due to premature treatment discontinuation or insufficient biopsy material or missing biopsy assessment at Week 40) by the count of HBsAg+ hepatocytes at baseline. In case the number of evaluated hepatocytes at Week 40 is available but the count of HBsAg+ hepatocytes is missing, both values will be replaced by baseline data. In case of missing biopsy assessment at baseline, no imputation will be performed, and those participants will not be included in the analysis.

5.3.1.2.4.2. Multiple Imputation

The secondary analysis of the primary endpoint will be repeated by using multiple imputation (MI) to impute any missing count of HBsAg+ hepatocytes at baseline and Week 40. Participants with missing biopsy assessments at both time points will not be included in the analysis.

The MI model will be applied to the continuous, logit-transformed proportions P_{ij}^{Obs} , as defined in Section 5.3.1.2.3. The model will be used separately for each panel, and will include the available non-missing logit-transformed proportions P_{ij}^{Obs} , and may include age, gender, log-transformed peripheral HBsAg at baseline and Week 40, and type of NA (TD/TAF versus ETV).

A planned total of 20 datasets will be generated for each panel. Depending on the amount of missing data, the number of imputed datasets to be generated may be increased appropriately to ensure robustness in the MI results and relative efficiency.

From each imputed dataset we will obtain values for P_{i0}^{Obs} , P_{i1}^{Obs} , and Δ_i^{Obs} . The distributions of these three quantities across the participants and imputed datasets will be described, both overall and by panel. The means of P_{i0}^{Obs} and P_{i1}^{Obs} will be obtained for each participant across imputed datasets and displayed in a spaghetti plot.

5.3.1.2.4.3. Per-Protocol Analysis (PP)

The primary and secondary analyses of the primary endpoint will be repeated with the PP set. All biopsy data will be used and only complete cases will be considered.

5.3.1.3. Subgroup Analyses

The potential association between the primary endpoint and baseline characteristics (Appendix 3) may be explored graphically using forest and scatter plots. The baseline subgroups of interest for efficacy are defined in Section 5.7.4.

The potential association between the primary endpoint and treatment-related characteristics may be explored both by using summary tables and plots. Subgroups in this category include:

- Received at least 1 dose of JNJ-6379 (No / Yes);
- Treatment with PegIFN- α 2a during study (No / Yes / Yes for 12 weeks / Yes for 24 weeks).

5.3.2. For Panel 3

5.3.2.1. Definition of Endpoints

The primary endpoints for Panel 3 are defined as the liver concentrations of JNJ-3989 (i.e., JNJ-3976, JNJ-3924, and M65), measured at treatment Weeks 12 and 40.

5.3.2.2. Primary Analysis

Individual listings and descriptive statistics (n, mean, SD, SE, median, minimum and maximum) for JNJ-3976 and JNJ-3924 liver and plasma concentrations, and M65 liver concentrations, as well as the ratio of liver to plasma concentrations at Weeks 12 and 40 will be provided. In addition, the ratio of M65 to JNJ-3976 at Weeks 12 and 40 will be calculated.

Scatterplots of individual JNJ-3976, JNJ-3924, and M65 liver concentrations by time point will be provided. Additionally, scatterplots of HBsAg change from baseline at Week 40 by JNJ-3976, JNJ-3924, and M65 liver concentrations at Week 40 will be provided.

